Patient safety will be monitored throughout the trial by the Investigator and supported by regular review by the Medical Monitor. The subject will be tested to ensure they do not have the Hepatitis B or C virus, thyroid function abnormalities or latent or active Tuberculosis, during the screening period for Part A. Chemistry and hematology laboratory values will be assessed under fasted conditions bi-weekly for the first month of the treatment period (Part A, Period 1 and Part B), followed by every 4 weeks through the remainder of the study (all Parts). Lipid levels will be assessed every 4 weeks throughout the study. In light of the COVID-19 pandemic, challenges in the conduct of study visits may arise from quarantines, site closures, and/or travel limitations. To ensure the safety of trial participants and to minimize risk to trial integrity, alternative methods for drug dispensation and assessments, including telemedicine visits and clinical laboratory blood draws at a local laboratory or via a Home Health Care agency, may be offered for those trial participants who may no longer have access to the investigational site. Significant cytopenias or other hematologic abnormalities will be managed by severity through dose interruption or discontinuation, and signs and symptoms of infection will be closely monitored and treated promptly. Patients who experience intolerable symptoms during treatment may discontinue treatment at the judgement of the Investigator, but will continue in the study and complete all assessments unless they withdraw consent. Patients may withdraw consent at any time.

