- 9. History of a lymphoproliferative disease or malignancy, other than non-melanoma skin cancer or cervical carcinoma. Patients with 3 or more basal or squamous cell carcinomas diagnosed in the past 2 years are excluded.
- 10. History of solid organ or hematological transplantation.
- 11. Fever, inflammation, or systemic signs of illness suggestive of systemic or invasive infection or a positive SARS-CoV-2 test result within 2 weeks prior to Baseline.
- 12. Abnormal levels of thyroid stimulating hormone at Screening, defined as <0.9 x the lower limit of normal (LLN) and >1.5 x the upper limit of normal (ULN).
- 13. Screening labs outside the normal range for parameters associated with potential risk for treatment under investigation. This will include but is not limited to:
 - a. Platelets $<100 \times 10^9/L$ or $>600 \times 10^9/L$
 - b. Absolute neutrophil count $\leq 1.5 \times 10^9/L$
 - c. Hemoglobin levels \leq 10.5 g/dL for females, or hemoglobin levels \leq 12.0 g/dL for males
- 14. Screening blood level of hemoglobin A1c ≥7.5% (58 mmol/mol, 9.3 mmol/L).
- 15. Abnormal liver function at Screening, defined as $\ge 2 \times ULN$ of serum alanine transaminase, serum aspartate transaminase, and serum alkaline phosphatase, or $\ge 1.5 \times ULN$ total bilirubin (unless isolated Gilbert's syndrome).

- 16. Abnormal renal function (estimated glomerular filtration rate <60 mL/min/1.73 m² using the CKD-EPI 2009 equation) at Screening.
- 17. Patient has positive results for hepatitis B surface antigens (HBsAg), antibodies to hepatitis B core antigens (anti-HBc), or hepatitis C virus (HCV) at Screening, or known history of human immunodeficiency virus infection. Subjects who test positive for HCV but who are in remission (sustained virologic response as evidenced by undetectable HCV RNA level using a sensitive assay≥ 12 weeks after completion of HCV therapy) are allowed inclusion in the study.
- 18. Vaccination with a live attenuated vaccine during the study or up to 6 weeks prior to randomization.
- 19. History of previous active disease due to *M. tuberculosis* (TB) without documentation of successful treatment; OR, patient has a positive result from a Tuberculin Skin Test (TST) or a QuantiFERON-TB Gold (QFT) test performed at Screening.

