11.10. Clinical Laboratory Assessments

Clinical laboratory assessments are presented in Section 18.1. Clinical laboratory samples should be collected at the beginning of each clinic visit and just prior to a dose on all Study Visit Days and will be processed by a central laboratory. In the event a patient is unable to attend an in-clinic visit due to COVID-19, clinical laboratory blood draws may be performed by a Home Health Care agency or a local laboratory. Patients should try to have laboratory blood draws performed in the morning and dose study drug after clinical laboratory blood draws are completed.

The results of clinical laboratory tests conducted at the Screening Visit (and prior to dosing) must be assessed by the Investigator to determine each patient's eligibility for participation in the study. The Investigator should indicate review of the laboratory reports throughout the study by signing and dating each report.

All clinical laboratory results that fall outside the reference range will be interpreted by the Investigator as Abnormal, not clinically significant, or Abnormal, clinically significant. Laboratory results deemed Abnormal, clinically significant will be recorded as an adverse event in the eCRF (see additional criteria outlined in Section 12.1). Clinically significant laboratory abnormalities indicative of hematologic or other effects requiring intervention should be discussed with the Medical Monitor(s). Additional tests and evaluations required to establish the significance or etiology of a clinically significant abnormal result or to monitor the course of an adverse event should be obtained when clinically indicated. Whenever possible, the etiology of the clinically significant abnormal findings will be documented on the eCRF.

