1/Synopsis/ Exclusion Criteria 9.2/Patient Exclusion Criteria	2. Treatment with other medications or agents within 1 month of Baseline or during the study that may affect hair regrowth or immune response, including but not limited to: corticosteroids administered orally, by injection, or applied to areas of skin affected by alopecia (intranasal and inhaled corticosteroids are allowed, eye and ear drops containing corticosteroids are also allowed); oral retinoids, oral cyclines (minocin, tetracycline); platelet-rich plasma injections; topical application to affected areas of retinoids, anthralin, squaric acid, diphenylcyclopropenone, or minoxidil.	2. Treatment with other medications or agents within 1 month of Baseline or during the study that may affect hair regrowth or immune response, including but not limited to: corticosteroids administered orally, intravenously or intramuscularly, or applied to areas of skin affected by alopecia (intranasal and inhaled corticosteroids are allowed, eye and ear drops containing corticosteroids are also allowed); oral retinoids, oral cyclines (minocin, tetracycline); platelet-rich plasma injections; topical application to affected areas of retinoids, anthralin, squaric acid, diphenylcyclopropenone, or minoxidil.	Exclusion criterion clarified
	11. Fever, inflammation, or systemic signs of illness suggestive of systemic or invasive infection within 2 weeks prior to first dose of study drug.	11. Fever, inflammation, or systemic signs of illness suggestive of systemic or invasive infection or a positive SARS-CoV-2 test result within 2 weeks prior to Baseline.	Exclusion criterion clarified due to SARS-CoV-2
	14. Screening blood level of hemoglobin A1c ≥7% (53 mmol/mol, 8.6 mmol/L).	14. Screening blood level of hemoglobin A1c ≥7.5% (58 mmol/mol, 9.3 mmol/L).	Exclusion criteria modified

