## 7. STUDY OPERATIONS

### 7.1. Protocol Deviations

A protocol deviation is any noncompliance with the clinical trial protocol or International Council for Harmonization of Technical Requirements for Pharmaceuticals for Human Use Good Clinical Practice requirements. The noncompliance may be either on the part of the participant, the investigator, or the study site staff. Protocol deviations will be recorded on the source documents and with an explanation for the deviation. All protocol deviations will also be recorded as specified in the monitoring plan.

Protocol deviations will be identified by site staff, through medical reviews, and by clinical research associates during site monitoring. Protocol deviations are reviewed by the sponsor on an ongoing basis during the study to classify deviations as minor or major. Deviations that may alter or confound interpretation of the study results will be classified as major deviations.

Protocol deviations will be summarized as counts and percentages by treatment group, deviation severity, and category for all randomized patients by study part. Reported deviation occurrence date will be compared to Part A Period 1 randomization date, Part A Period 2 randomization date, and Part B re-randomization date to determine the study part where the deviation will be summarized.

Deviations will also be presented by patient in a data listing for all randomized patients.

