Finally, the count and percentage of abnormal laboratory values per parameter, where applicable, will be provided. Additionally, a listing of patients with Abnormal laboratory values will be provided.

These analyses will be repeated for serum chemistry results, hematology results, and lipid results (where lipid tests include total cholesterol, low-density lipoprotein, high-density lipoprotein, and triglycerides). Laboratory results will also be listed. Reference ranges for each clinical laboratory parameter will also be summarized in a data listing.

Pregnancy test results will be listed only.

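### Exclusion criterion 12 joins its two TSH limits with *and*; read literally it excludes nobody, and it should say *or*

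*Protocol*

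**What the plan says.** Item 12 of the exclusion criteria (Protocol Section 9.2) covers "Abnormal levels of thyroid stimulating hormone at Screening", and sets the limits as "defined as <0.9 x the lower limit of normal (LLN) and >1.5 x the upper limit of normal (ULN". The Synopsis carries the same text. Footnote 12 to Table 1 (Schedule of Assessments: Part A) schedules TSH at Screening only.

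Three other places bear on the meaning:

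- **Purpose.** Section 8.1, under Safety, states: "The subject will be tested to ensure they do not have the Hepatitis B or C virus, thyroid function abnormalities".
- **A parallel criterion.** Item 13a of Section 9.2 excludes platelets below 100 *or* above 600 x 10^9/L.
- **Investigator review.** Section 11.10 states: "The results of clinical laboratory tests conducted at the Screening Visit (and prior to dosing) must be assessed by the Investigator", so as to decide eligibility.

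The SAP does not restate the TSH criterion.

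**The concern.** The two limits sit at opposite ends of the TSH scale and apply to one measurement at one visit. If *and* is taken as a logical conjunction, a patient is excluded only when a single value is too low and too high at once, which cannot happen. An operative safety threshold would then have no effect. A patient with marked hypothyroidism or hyperthyroidism would pass item 12, and no later TSH test is scheduled that would show it. The most that is at stake is the eligibility of patients with abnormal thyroid function, and whether sites and monitors apply the same rule. No analysis depends on it.

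**Working it through.** No figure in the plan needs reproducing. The check is one of logic, followed by a comparison of texts.

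**Inputs.** Lower cut-off 0.9 x LLN and upper cut-off 1.5 x ULN (Section 9.2, item 12). The only assumption is that the laboratory's reference range satisfies 0 < LLN < ULN.

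**Step 1: the rule as a conjunction.** Ordering the four quantities gives

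0.9 x LLN < LLN < ULN < 1.5 x ULN.

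The ratio of the cut-offs is (1.5 x ULN) / (0.9 x LLN) = (1.5 / 0.9) x (ULN / LLN) = 1.67 x (ULN / LLN), which exceeds 1.67 because ULN / LLN > 1. The set of values below 0.9 x LLN and the set above 1.5 x ULN do not overlap, so the number of TSH values meeting both conditions is 0, whatever the laboratory's range.

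**Step 2: the rule with *or*.** The excluded set is every value below 0.9 x LLN together with every value above 1.5 x ULN. Values from 0.9 x LLN to 1.5 x ULN remain eligible on this item. This is a workable two-sided rule with some tolerance outside the normal range at each end.

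**Step 3: which was meant.**

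| Place | What it shows |
|---|---|
| Section 8.1, Safety | Thyroid testing is there to rule out abnormal function; a rule nobody can meet does not do that |
| Section 9.2, item 13a | Low and high limits on one analyte, joined with *or* |
| Section 9.2, item 12, and Synopsis | Low and high limits on one analyte, joined with *and* |

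Items 12 and 13a are the only two-sided limits on a single analyte in Section 9.2, and they use different connectors.

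**Step 4: has it been corrected elsewhere?** The Amendment 2 summary of changes lists new wording for exclusion items 2, 11, 14, 17, 18 and 19, which is 6 of 27. Item 12 is not among them, and no other summary of changes lists it. This does not prove an error. It shows only that no listed change touched item 12, and the current text still says *and*.

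**Step 5: do other criteria supply the limits?** Item 13 refers to Screening laboratory values outside the normal range for parameters associated with risk, and is not confined to those it names. Item 27 covers clinically significant conditions in the Investigator's judgement. Neither gives a TSH limit. Item 13, if applied to TSH, would work from the normal range itself, which differs from the band of 0.9 x LLN to 1.5 x ULN. That band appears only in item 12.

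**The case against.** The strongest reply is that nobody would read the item as a conjunction. It speaks of abnormal levels in the plural and then names two ranges, so *and* can simply list two kinds of abnormality; the other reading is impossible on its face. Item 15 has a similar form and uses a loose *and* across three liver enzymes, which suggests a drafting habit. This is a fair account of how the wording arose and of how sites probably read it, though the documents do not record what sites did. It does not make the text correct: a numeric eligibility limit should not rely on the reader discarding its literal meaning.

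The second reply is that Investigator review under Section 11.10 and items 13 and 27 would catch a patient with real thyroid disease. This stands as a limit on the consequence. It does not restore the specific thresholds.

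The third reply is that amending may come too late. The Synopsis estimates last patient completion in June 2023 and participation of up to about 80 weeks. Counting back 80 x 7 = 560 days from June 2023 puts the last patient's screening at about November to December 2021, before Amendment 3 of 09 September 2022. These are planned dates, so closure of enrolment is inferred and not documented. If it is right, amending item 12 would change no eligibility decision, and only a clarification in the report remains useful.

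**Conclusion.** The criterion is wrong as written. Taken literally it excludes 0 patients under any reference range with LLN below ULN, against the purpose stated in Section 8.1. The wording stands in 2 places, and no other text supplies the intended limits.

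The consequence is minor. The sensible reading is easy to reach, Screening results are reviewed by the Investigator, and TSH enters no endpoint or planned safety summary; no display title in SAP Section 15.4 names it. Nothing in the documents shows that a patient was wrongly enrolled, and no effect on sample size or efficacy estimates follows. Confidence is high on the logic. On practical impact the documents give no evidence either way.

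**What to change.** Replace *and* with *or* between the two TSH limits in item 12, in both Section 9.2 and the Synopsis, by amendment or administrative letter. If enrolment has closed, state in the study report that the item was meant to exclude Screening TSH below 0.9 x LLN or above 1.5 x ULN, and that the printed connector is an error.

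The cost is one word in two places, or one sentence in the report. No patient procedure, data collection or analysis changes. A dedicated TSH display is not needed: no analysis uses the result, and Protocol Section 18.1 places TSH under its Other heading, outside the chemistry, hematology and lipid groups that SAP Section 9.5 reports. Should a patient with TSH outside the intended limits come to light, the sponsor's existing review under SAP Section 7.1 can classify the deviation.

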2. SYNOPSIS

Name of Sponsor/Company:

Concert Pharmaceuticals, Inc.

Name of Investigational Product:

CTP-543

Name of Active Ingredient:

D8- ruxolitinib; 1*H*-Pyrazole-1-propanenitrile, β-(cyclopentyl-2,2,3,3,4,4,5,5- d_8)-4-(7*H*-pyrrolo[2,3-d]pyrimidin-4-yl)-, (βR)-, phosphate

Title of Study:

A Study to Evaluate Maintenance of Hair Regrowth Following Dose Reduction of CTP-543 in Adult Patients with Moderate to Severe Alopecia Areata

Phase of development: 2

Study center(s): Multicenter study; approximately 25 sites; US

Studied period (years):

Estimated date first patient enrolled: February 2021

Estimated date last patient completed: June 2023

Objectives:

The primary objective of the study is to assess the effects of dose reduction or drug discontinuation subsequent to hair regrowth following 24 weeks of treatment with either 8 mg BID or 12 mg BID of CTP-543 in adult patients with moderate to severe alopecia areata.

The secondary objective of the study is to assess the effects of drug re-treatment following dose reduction or drug discontinuation with the original CTP-543 dose (either 8 mg BID or 12 mg BID) in patients who have not maintained hair regrowth.

Methodology:

This is a two part, double-blind, randomized, multicenter study to evaluate the regrowth of hair with CTP-543 and subsequent durability of that regrowth following dose reduction or drug discontinuation in adult patients with moderate to severe alopecia areata. Patients will be between 18 and 65 years of age and experiencing an episode of hair loss associated with alopecia areata lasting at least 6 months and not exceeding 10 years. Patients not currently being treated for alopecia areata or with other treatments that might affect hair regrowth or immune response must have at least 50% hair loss as measured by the Severity of Alopecia Tool (SALT) at Screening and Baseline.

The study is divided into 2 Parts:

Part A: Period 1 (Treatment Phase) and Period 2 (Dose Modification Phase)

Part B: Re-Treatment Phase

Part A

Period 1

Patients will be screened up to 28 days prior to initiation of study drug. Patients will provide appropriately-obtained informed consent prior to initiating any screening procedures. Patients meeting initial screening criteria will be eligible to continue to the Day 1 (Baseline) visit for review of eligibility

[figure not shown]

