- 14. Screening blood level of hemoglobin A1c ≥7.5% (58 mmol/mol, 9.3 mmol/L).
- 15. Abnormal liver function at Screening, defined as $\ge 2 \times ULN$ of serum alanine transaminase, serum aspartate transaminase, and serum alkaline phosphatase, or $\ge 1.5 \times ULN$ total bilirubin (unless isolated Gilbert's syndrome).
- 16. Abnormal renal function (estimated glomerular filtration rate <60 mL/min/1.73 m² using the CKD-EPI 2009 equation) at Screening.
- 17. Patient has positive results for hepatitis B surface antigens (HBsAg), antibodies to hepatitis B core antigens (anti-HBc), or hepatitis C virus (HCV) at Screening, or known history of human immunodeficiency virus infection. Subjects who test positive for HCV but who are in remission (sustained virologic response as evidenced by undetectable HCV RNA level using a sensitive assay≥ 12 weeks after completion of HCV therapy) are allowed inclusion in the study.
- 18. Vaccination with a live attenuated vaccine during the study or up to 6 weeks prior to randomization.
- 19. History of previous active disease due to M. tuberculosis (TB) without documentation of successful treatment; OR, patient has a positive result from a Tuberculin Skin Test (TST) or a QuantiFERON-TB Gold (QFT) test performed at Screening.
 - NOTE: If the patient has a positive QFT result at Screening and: (1) has no history of successful treatment for either active disease or latent infection due to M. tuberculosis, or (2) currently resides in an area with low prevalence of tuberculosis, or (3) has no lifetime history of occupational or household exposure to person(s) with tuberculosis, then the initial Screening QFT result may be a false-positive. In this instance, a second Screening test for latent TB infection should be obtained either: (1) a repeat QFT test or (2) a Tuberculin Skin Test (TST). The repeat QFT test must be negative or the TST should show <15mm induration (considered negative TST) before being considered eligible for the study.
- 20. History of prolonged QT syndrome or a Screening QTc interval with Fridericia's correction (QTcF) > 450 msec for males or QTcF > 470 msec for females.
- 21. History of alcohol, medication, or illicit drug abuse within 1 year before the first dose of study drug.
- 22. Females who are nursing, pregnant, or planning to become pregnant while in the study, and for 30 days after last dose of study drug.

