 - NOTE: If the patient has a positive QFT result at Screening and: (1) has no history of successful treatment for either active disease or latent infection due to M. tuberculosis, or (2) currently resides in an area with low prevalence of tuberculosis, or (3) has no lifetime history of occupational or household exposure to person(s) with tuberculosis, then the initial Screening QFT result may be a false-positive. In this instance, a second Screening test for latent TB infection should be obtained either: (1) a repeat QFT test or (2) a Tuberculin Skin Test (TST). The repeat QFT test must be negative or the TST should show <15mm induration (considered negative TST) before being considered eligible for the study.
- 20. History of prolonged QT syndrome or a Screening QTc interval with Fridericia's correction (QTcF) > 450 msec for males or QTcF > 470 msec for females.
- 21. History of alcohol, medication, or illicit drug abuse within 1 year before the first dose of study drug.
- 22. Females who are nursing, pregnant, or planning to become pregnant while in the study, and for 30 days after last dose of study drug.
- 23. Participation in another investigational study within the greater of 4 weeks or 5 half-lives of an investigational medication prior to screening or during the study.
- 24. Use of strong cytochrome P450 3A4 (CYP3A4) inhibitors (such as, but not limited to clarithromycin, conivaptan, grapefruit juice, indinavir, itraconazole, ketoconazole, lopinavir/ritonavir, mibefradil, nefazodone, nelfinavir, posaconazole, saquinavir, telaprevir, telithromycin, voriconazole, or fluconazole) dosed for systemic exposure.
- 25. Use of strong CYP3A4 inducers (such as, but not limited to barbiturates, carbamazepine, efavirenz, glucocorticoids, modafinil, nevirapine, oxcarbazepine, phenobarbital, phenytoin, pioglitazone, rifabutin, rifampin, St. John's Wort, or troglitazone) dosed for systemic exposure.
- 26. Donation of blood > 499 mL of blood or plasma within 56 days of Screening (during a clinical trial or at a blood bank donation) and for 30 days after last dose of study drug.
- 27. Clinically significant medical condition, psychiatric disease, or social condition, as determined by the Investigator, that may unfavorably alter the risk-benefit of study

participation, adversely affect study compliance, or confound interpretation of study results

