18.4.2. Quality of Hair Patient Reported Outcome (QPRO)

For the next set of questions, please choose the best answer that represents how you feel today.

1.	How satisfied are you with the	∫ Very	4 Dissatisfied	3∐ Neither	2 Satisfied	¹∐ Very
	thickness of the hair on your	dissatisfied		satisfied nor		satisfied
	scalp?			dissatisfied		
2	How satisfied are you with the	5	4	3	2	1
۷.	•	Very	Dissatisfied	Neither	Satisfied	Very
	evenness of the hair on your	dissatisfied		satisfied nor		satisfied
	scalp?			dissatisfied		
		5	4	3	2	1
3.	How satisfied are you with your	Very	Dissatisfied	Neither	Satisfied	Very
	eyebrows?	dissatisfied		satisfied nor		satisfied
				dissatisfied		
		5	4	3	2	1
4.	How satisfied are you with your	Very	Dissatisfied	Neither	Satisfied	Very
	eyelashes?	dissatisfied		satisfied nor		satisfied
	•			dissatisfied		

1. SUMMARY OF CHANGES: AMENDMENT 2 (23 February 2021)

Section	Previous Text	New Text	Reason for Revision

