	19. Positive TB test, or history of incompletely treated or untreated tuberculosis. Note: TB test may be performed via a QuantiFERON-TB Gold test or a Tuberculin Skin Test (TST). If the TST is negative, patients can be randomized into the study, assuming they meet all other inclusion and exclusion criteria. If results are equivocal, or there is reason to believe the result is a false positive, a QuantiFERON-TB Gold must be performed before a patient is eligible for randomization.	19. History of previous active disease due to M. tuberculosis (TB) without documentation of successful treatment; OR, patient has a positive result from a Tuberculin Skin Test (TST) or a QuantiFERON-TB Gold (QFT) test performed at Screening. NOTE: If the patient has a positive QFT result at Screening and: (1) has no history of successful treatment for either active disease or latent infection due to M. tuberculosis, or (2) currently resides in an area with low prevalence of tuberculosis, or (3) has no lifetime history of occupational or household exposure to person(s) with tuberculosis, then the initial Screening QFT result may be a false-positive. In this instance, a second Screening test for latent TB infection should be obtained – either: (1) a repeat QFT test or (2) a Tuberculin Skin Test (TST). The repeat QFT test must be negative or the TST should show <15mm induration (considered negative TST) before being considered eligible for the study.	Exclusion criterion clarified

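### Exclusion 19's NOTE joins its three false-positive conditions with 'or', so known TB exposure does not block the retest for a QFT-positive patient with no prior TB treatment and no prior active TB

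*Protocol*

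**What the plan says.** Protocol Section 9.2, item 19, has two grounds for exclusion: prior active TB "without documentation of successful treatment; OR, patient has a positive result from a Tuberculin Skin Test (TST") or a QFT at Screening. The NOTE then qualifies a positive QFT. Its first two conditions are "1) has no history of successful treatment for either active disease or latent infection due to M. tuberculosis, or (2) currently resides" in an area of low TB prevalence. The third is "or (3) has no lifetime history of occupational or household exposure to person(s) with tuberculosis". If the list is satisfied, "then the initial Screening QFT result may be a false-positive"; these words stand in 9.2 and in the new text listed for Amendment 2. A second test is then to be obtained, with this requirement: "The repeat QFT test must be negative or the TST should show <15mm induration (considered negative TST) before being considered eligible".

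The Synopsis carries the same connectors: "2) currently resides in an area with low prevalence of tuberculosis, or (3) has no lifetime history of occupational or household exposure". No other section makes the three conditions cumulative.

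Four other provisions bear on the point:
- Section 8.1 gives the purpose of screening as making sure that subjects have neither latent nor active TB.
- Section 11.1 collects infection exposure risk as part of the medical history.
- Table 1 marks the tuberculosis test at Screening only, and Table 2 (Part B) has no such row.
- Section 11.7 includes TB signs and symptoms in both full and brief examinations.

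**The concern.** The NOTE lists reasons to doubt a positive QFT. Known household or occupational exposure is a reason to believe it, and condition (3) appears to be there to take account of that. Because the connector is 'or', condition (3) can only help to open the retest and can never close it when condition (1) or (2) is met. Condition (1) is met by every patient who has never been treated for TB.

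The resulting rule is hard to defend. The only profile it refuses is the successfully treated patient who lives outside a low-prevalence area and has been exposed. A never-treated patient with the same residence and the same exposure gets the retest.

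One negative second result then overrides the positive one. The NOTE asks for no Medical Monitor consultation, whereas the NOTE to Exclusion 3 suggests one where questions arise about prior JAK-inhibitor tolerability. What is at stake is a patient with latent TB starting a JAK inhibitor. Section 11.1 itself refers to the drug class's potential immunosuppressive properties. No later test for latent infection is scheduled.

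**Working it through.** The plan gives no figure to reproduce. The check is a truth table for a QFT-positive patient.

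Inputs, all from the item 19 NOTE: (1) no history of successful TB treatment; (2) residence in a low-prevalence area; (3) no lifetime household or occupational exposure. T means the condition is met. Patients with prior active TB and no documented treatment are outside the table, because item 19's first clause excludes them regardless.

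| (1) | (2) | (3) | As written: 'or' | [(1) or (2)] and (3) | All joined by 'and' |
|---|---|---|---|---|---|
| T | T | T | open | open | open |
| T | T | F | open | closed | closed |
| T | F | T | open | open | closed |
| T | F | F | open | closed | closed |
| F | T | T | open | open | closed |
| F | T | F | open | closed | closed |
| F | F | T | open | closed | closed |
| F | F | F | closed | closed | closed |
| **Open** | | | **7 of 8** | **3 of 8** | **1 of 8** |

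Reading off the groups:

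- Never treated, (1) true: open in 4 of 4 as written, 2 of 4 with (3) mandatory, 1 of 4 with 'and' throughout.
- Never treated and exposed, (1) true and (3) false: open in 2 of 2 as written, 0 of 2 under either alternative. This is the group at issue.
- Never treated and not exposed, (1) and (3) true: open in 2 of 2 as written, 2 of 2 with (3) mandatory, 1 of 2 with 'and' throughout.
- Successfully treated, (1) false: open in 3 of 4 as written, 1 of 4 with (3) mandatory, 0 of 4 with 'and' throughout.

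These are counts of rule profiles. They are not weighted by how often each profile occurs and do not estimate how many patients are affected.

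**The case against.** The strongest reply is that the conditions open a retest, not entry. Every QFT-positive patient must still produce a negative repeat QFT or a TST under 15 mm, and offering a second test to anyone with one reason to doubt the first is a coherent policy. Exposure is not ignored either: it is collected under 11.1, and item 27 lets the investigator exclude on risk-benefit grounds. Examinations that check for TB signs are marked at Weeks 4, 8, 12, 16, 20, 24, 32, 36, 40, 44 and 48 and in Part B. Remote examinations ask about TB exposure (11.7), and Unscheduled Visits can be held on suspicion of TB (11.11).

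All of that stands as a limit on harm. It does not close the route. No provision ties exposure to the retest, item 27 does not mention TB, and an examination for signs and symptoms is not a test for latent infection.

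A reader might infer three stronger things that the documents do not support:

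- That 'and' was intended throughout. Nothing says so; Amendment 2 introduced the same 'or' wording as its new text.
- That nearly all patients were screened under this wording, because Amendment 2 is dated 23 February 2021 and first enrolment was planned for that month. Section 14.4 makes sites wait for IRB approval before implementing a non-administrative amendment, so the date of use at each site is unknown.
- That affected patients would typically be dosed for 72 weeks. That is the maximum (24 + 24 + 24). About 2 × 50 = 100 of 300 patients are expected to enter Period 2, half of them assigned to placebo for that period. About 200 would finish study treatment at Week 24, although they may join the extension study.

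**Conclusion.** The point holds as a defect in a screening-safety rule. For a QFT-positive patient with no prior TB treatment and no prior active TB, condition (1) is always met, and known household or occupational exposure does not block the retest. This fits poorly with the aim stated in Section 8.1.

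Its size in patients cannot be derived. The documents give no number of QFT-positive or retested patients, so the number affected is unknown. That it is small is my assumption, based on the US-only sites. The finding does not show that any infected patient was enrolled, and it changes no endpoint, analysis or statistical result. It rests on reading the connectors literally, which is how a site would apply them. It is worth correcting because the change is short and specific.

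**What to change.** In item 19's NOTE, make condition (3) mandatory in both Section 9.2 and the Synopsis, for example '[(1) or (2)] and (3)'. This closes the retest to exposed patients and keeps it for every never-treated, unexposed patient. Joining all three with 'and' is a stricter option, but it bars every successfully treated patient from a retest, and the documents do not show that this is wanted.

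The cost is a short wording change in two places and a note to sites. The price in eligibility is that exposed QFT-positive candidates lose the retest (three profiles in the table), as does one unexposed profile: the successfully treated patient outside a low-prevalence area. If the sponsor wishes to keep that last profile, requiring (3) alone would do so.

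The documents do not say whether screening has closed. If the last patient completes on 30 June 2023 after the full 80 weeks (560 days), that patient's screening starts on 17 December 2021, before Amendment 3 of 09 September 2022. In that case the rewording serves mainly late enrolment or reuse of the text. The live action is then for the Medical Monitor to review the exposure history already collected under 11.1 for patients enrolled after a positive QFT who are still on study drug. This is a bounded review that needs no new data collection.
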